5 STUDY TREATMENTS

5.1 Description of Treatments

5.1.2 Placebo or Control

Not applicable.

5.1.3 R₀1 Knottin PET tracer

The Knottin PET tracer is not considered a study treatment but is an investigational tool used during the PET procedure for obtaining the computerized images necessary for this trial.

The Knottin tracer, also known as $[^{18}F]FP-R_01-MG-F2$ is formulated in a sterile and pyrogen-free isotonic solution and is administered as a single slow IV injection. Refer to the Radiology Manual for details.

5.2 Treatments Administered

[figure not shown]
Participants will receive a single dose of 60 mg

120, 240 or 320 mg of PLN-74809. Eligible participants consenting to participate will receive up to four single doses of PLN-74809 (on different occasions).

Study drug will be dispensed by the site pharmacist. Refer to the Pharmacy Manual for details.

5.3 Selection and Timing of Dose for Each Participant

Confidential Page 301 of 331

5.6 Blinding

This is an open-label study.

5.7 Concomitant Therapy

Treatment with current standard of care (nintedanib or pirfenidone) for IPF is allowed provided these drugs have been given at a stable dose for at least 3 months before initiation of Screening and are expected to remain unchanged during the study.

Treatment for IPF (fibrosis) with any other non-FDA-approved agent is not permitted during the study. Treatments to address IPF disease symptoms, (cough, gastroesophageal reflux disease, etc) are allowed.

Confidential Page 302 of 331

Treatment with another investigational drug, investigational device, or approved therapy for investigational use within 30 days or 5 half-lives (whichever is longer) before anticipated dosing is prohibited apart from PLN-74809.

Other medications to provide reasonable patient care of IPF or other comorbidities are allowed during the study; however, these should only be used if necessary because, at this stage of development, no formal drug-drug interaction studies with PLN-74809 have been performed.

During screening, all medications, including over-the-counter medications and herbal supplements, taken during the 30 days prior to Screening will be recorded and reviewed by the Principal Investigator (PI) in consultation with the Medical Monitor to determine whether the participant is suitable for inclusion. For other concomitant medications that are needed during the study conduct, the PI should consult with the Medical Monitor as soon as feasible.

If used, all concomitant medications, including both prescription and nonprescription drugs, should first be discussed with the PI and Medical Monitor before administration. This requirement does not apply in the case of urgent, necessary treatment of adverse events (AEs). In all cases, all medications, including over-the-counter medications and herbal supplements, that are taken by participants during the course of the study will be recorded using the generic name of the medication. In addition, for participants who are receiving nintedanib or pirfenidone, the time of drug administration should be collected on each day on which samples are obtained for assessing PLN-74809 PK.

5.8 Restrictions

5.8.1 Prior Therapy

Previous use of IPF standard-of-care treatment (pirfenidone or nintedanib) is allowed for participation in this study. Prohibited medications (see Section 5.7, Concomitant Therapy) should be stopped at least 5 half-lives before dosing on Day 1.

5.8.2 Fluid and Food Intake

5.8.3 Participant Activity Restrictions

Smoking of any kind is not permitted within 3 months of Screening or during the study.

Confidential Page 303 of 331

5.8.4 Contraception

Female participants of childbearing potential (i.e., ovulating or premenopausal and not surgically sterile) and all male participants with sexual partners of childbearing potential must use highly effective methods of birth control during their participation in the study and for 90 days after the last administration of study drug. Highly effective methods of birth control are defined as those with 99% or greater efficacy

Acceptable methods of contraception for female and male participants enrolled in the study include the following:

- Complete abstinence from sexual intercourse if this is the participant's usual and preferred lifestyle
- Implanted contraceptives
- Oral hormonal contraceptives if using for 1 year or more
- Dual method of contraception:
 - o Condom in conjunction with use of an intrauterine device
 - o Condom in conjunction with use of a diaphragm
 - Oral hormonal contraceptives with less than 1 year of use in conjunction with condom
- Sexual partner with surgical sterilization (e.g., vasectomy, tubal ligation, hysterectomy and/or bilateral oophorectomy).

Females who are using hormonal contraceptives should have started use at least 12 weeks before Screening.

Participants must agree to abstain from egg or sperm donation and to continue condom use through 30 or 90 days, respectively, after administration of the last dose of study drug.

5.8.5 Diet and Other Restrictions

There are no specific dietary restrictions.

Smoking and vaping are not permitted during the study. Use of recreational drugs and/or abuse of alcohol consumption are not permitted during the study.

5.9 Treatment Compliance

Dosing will be performed in the presence of site staff. Site staff will ensure the full dose amount is taken. Participants who are receiving nintedanib or pirfenidone will be provided with a dosing log in which they will collect dosing information on the day before and the day of study drug dosing.

5.10 Packaging and Labeling

Confidential Page 304 of 331

5.11 Storage and Accountability

Confidential Page 305 of 331

6 STUDY PROCEDURES

6.1 Informed Consent

An informed consent form (ICF) describing the study and all anticipated risks of participation will be prepared and submitted to the institutional review board (IRB) for approval. Written and dated informed consent will be obtained from each study participant prior to any study-related procedures being performed.

6.2 Medical History

Medical history will be reviewed and recorded at Screening.

6.3 Demographic Information

[figure not shown]
Date of birth, sex, ethnicity, and race will be recorded at Screening. Body weight and height will be measured with the participant in light clothing. Weight will be recorded in kilograms and height will be recorded in centimeters.

6.4 Physical Examination

Complete and directed physical examinations will be performed at the time points specified in the Schedule of Events (Appendix 1). Complete physical examinations include general appearance, head, ears, eyes, nose, throat, dentition, thyroid, chest (heart, lungs), abdomen, skin, neurological, extremities, back, neck, musculoskeletal, and lymph nodes. Directed physical examination includes head, ears, eyes, nose, throat, heart, lungs, abdomen, skin, musculoskeletal, and lymph nodes and any pertinent system based on any prior findings. Physical examinations may be performed at various unscheduled time points if deemed necessary by an Investigator.

6.5 Vital Signs

Blood pressure and heart rate will be recorded after participants have rested for at least 3 minutes in a supine position. Ear temperature will be measured and peripheral capillary oxygen saturation (SpO₂) will be measured using a finger pulse oximeter.

Confidential Page 306 of 331

6.7 Clinical Laboratory Tests

Participants will be in a seated or supine position during blood collection. Clinical laboratory tests will include hematology, clinical chemistry, and urinalysis. Safety laboratory tests (hematology and clinical chemistry) will be collected from fasting (at least 2 hours) participants where appropriate.

Urine pregnancy tests will be performed on all women at Baseline prior to the dose of study drug and, if positive, will be confirmed by a blood pregnancy test.

A detailed list of laboratory tests is provided in Appendix 2.

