| Study Design: | This is an open-label study in which up to 12 participants with IPF will receive up to two doses of PLN-74809, starting at 60 mg or 80 mg (and also be evaluated). Higher planned doses, including 120 mg, 240 mg and 320 mg, will also be evaluated All participants will undergo PET imaging at Baseline and on the day of PLN-74809 dosing. Eligible participants consenting to receive a maximum of four single doses (on different occasions) of PLN-74809 (e.g., 60 mg and 120 mg) will need to undergo a \geq 14-day washout between doses and will not need to repeat the Baseline PET imaging. Additionally, if in the opinion of the Investigator, there is no clinical decline within 60 days only hematology and clinical chemistry assessments should be completed; other Screening and Baseline procedures are not required. If the PET ligand cannot be successfully synthetized on the scheduled day, participants will wait at least 1 week until another dose of PLN-74809 is administered. Participants will undergo no more than 3 PET imaging scans (Baseline and up to 2 scans post PLN-74809 dosing). All PET imaging will be performed using the Ro1 Knottin tracer, as generated by the radiology department at Stanford Medical Center. Post-dose PET imaging for the assessment of $\alpha_{\rm V}\beta_{\rm f}$ receptor occupancy will be performed \geq 4 hours postdose, to coincide with PLN-74809 time to maximum observed drug concentration ($T_{\rm max}$; \sim 4 hours after the administration of study drug). | |

Confidential Page 277 of 331

| | Blood samples for PLN-74809 pharmacokinetics (PK) will be obtained before and at 0.5, 1, 2, 3 and 4 hours postdose on Day 1 (prior to administration of the PET ligand) and at 24 hours postdose (Day 2). Biomarker blood samples will be collected as per the Schedule of Assessments. Forced vital capacity (FVC) and diffuse capacity for carbon monoxide (DLco) will be performed on all participants at Screening for inclusion/exclusion purposes; a historical FVC and DLco within 1 month of screening may be used. For those participants whose travel to the study center would prohibit study participation, housing accommodation may be provided by the Sponsor. Except for the previously described periods, participants will be allowed to return to their homes between study visits. |
|---|---|

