3 INVESTIGATIONAL PLAN

3.1 Overall Study Design and Plan

| This study is an open-label study in which up to 12 participant | ts with IPF will receive up to |
|---|----------------------------------|
| two doses of PLN-74809, starting at 60 mg | or 80 mg |
| Higher planned doses, including 120 mg, 240 mg | g, and 320 mg, will also be |
| evaluated | |
| All participants will undergo PET imagi | ing at the Baseline Visit and or |
| the day of PLN-74809 dosing. | |

Eligible participants consenting to receive a maximum of 4 different doses of PLN-74809 (e.g., 60 mg and 120 mg) will need to undergo a ≥14-day washout between doses, and not have to repeat Baseline PET imaging. Additionally, if in the opinion of the Investigator, there is no clinical decline, the other Screening and Baseline procedures do not have to be repeated. If the PET ligand cannot be successfully synthetized on the scheduled day, participants will wait at least 1 week before another dose of PLN-74809 is administered.

All PET imaging will be performed using the R_01 Knottin tracer, as generated by the radiology department at Stanford Medical Center. Post-dose PET imaging, for the assessment of $\alpha_v \beta_6$ receptor occupancy, will be performed to coincide with PLN-74809 time to maximum observed drug concentration (T_{max} ; ~4 hours after the administration of study drug). Participants will undergo no more than 3 PET imaging scans (Baseline and up to 2 scans post PLN-74809 dosing).

Blood samples for PLN-74809 PK will be obtained before and at 0.5, 1, 2, 3, and 4 hours after dosing on Day 1 and at 24 hours after dosing (Day 2).

[figure not shown]
Forced vital capacity (FVC) will be performed on all participants at Screening for inclusion/exclusion purposes.

Except for the previously described periods, participants will be allowed to return to their homes between study visits.

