Appendix 1 Schedule of Events

| Study Period | Screening ^{m,n} | Baseline ^{m,n} | | | Dosin | g Day | | | Day 2 (or | EoT/EoS/ET |
|---|--------------------------|-------------------------|----------------|-----|---------|-------|-----|-----|------------|-----------------------------------|
| Study Day | Day -35 to Day -8 | Day -7 | | Da | ay 1 (o | r Day | 8ª) | | Day 9) | Day 8 (or Day 15) (±2 days) |
| Hours after Dose | | | 0 _p | 0.5 | 1 | 2 | 3 | 4 | | |
| Informed consent, medical history, demographics | • | | | | | | | | | |
| Check inclusion exclusion criteria | • | • | S | | | | | | | |
| Physical examination ^c | • | • | • | | | | | | | • |
| Vital signs (post 3 minutes, supine) | • | • | • | | | . 08 | | | | • |
| | | | | | | | | | | |
| Hematology and clinical chemistry ^d | • | • | • | | | | | | • | •° |
| Urinalysis ^e | • | • | • | | | | | | | • |
| Urine pregnancy test (females only) | | • | | | | | | | | |
| FVC | • | 163 | | | | 12 | | | | |
| DLco | • | | | | | | | | | |
| Volumetric HRCT (quantitative)f | • | | | | | | | | | |
| PET imaging | | • | | | | 100 | | ● g | | |
| Blood samples for radiotracer PK | | • | | | | | | ● h | | |
| | | | | | | | | | | |
| Study drug administration (PLN-74809)i | | 5,3 | • | | | | | | | |
| Blood sample for PLN-74809 PK d | | | • | • | • | • | • | • | ● j | |
| | | | | | | | | | | |
| Adverse events ¹ | • | • | • | • | • | • | • | • | • | • |
| Concomitant medications 1 | • | • | • | • | • | • | • | • | • | • |

; EoT = end of treatment; EoS = end of study; ET = early termination; FVC = forced vital capacity; HRCT = high-resolution computerized tomography; PET = positron emission tomography; PK = pharmacokinetic.

Page 325 of 331

In case the PET ligand cannot be successfully synthetized on the scheduled day, participants will wait at least 1 week and then be dosed again for a

Pliant Therapeutics Inc.

Page 51

- a In case the PET ligand cannot be successfully synthetized on the scheduled day, participants will wait at least 1 week and then be dosed again for a second attempt at PET synthesis and imaging.
- b Time 0 refers to immediately pre-dose.
- Complete physical examination at Screening and directed physical examination thereafter.
- d A table of blood volumes is provided in Appendix 3.
- Urinalysis: dipstick followed up by microscopic examination if needed.

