## 1.1 Schedule of Events

| Study Period                                       | Screening m,n | Baseline m,n | Dosing Day        |        |                                |   |   | Day 2 (or Day 9) | EoT/EoS/ET     |  |
|--|--------------------------|-------------------------|-------------------|--------|--------------------------------|---|---|------------------|----------------|--|
|  |                          |                         | Day -35 to Day -8 | Day -7 | Day 1 (or Day 8 a ) |   |   |                  |                |  |
| Study Day  | Hours after Dose         |                         | 0 b    | 0.5    | 1                              | 2 | 3 | 4                |                |  |
| Informed consent, medical history, demographics    | ●                        |                         |                   |        |                                |   |   |                  |                |  |
| Check inclusion exclusion criteria                 | ●                        | ●                       |                   |        |                                |   |   |                  |                |  |
| Physical examination c                  | ●                        | ●                       | ●                 |        |                                |   |   |                  | ●              |  |
| Vital signs (post 3 minutes, supine)               | ●                        | ●                       | ●                 |        |                                |   |   |                  | ●              |  |
|     |                          |                         |                   |        |                                |   |   |                  |                |  |
| Hematology and clinical chemistry d     | ●                        | ●                       | ●                 |        |                                |   |   | ●                | ● e |  |
| Urinalysis e                            | ●                        | ●                       | ●                 |        |                                |   |   |                  | ●              |  |
| Urine pregnancy test (females only)                |                          | ●                       |                   |        |                                |   |   |                  |                |  |

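### On the readable text the only scheduled pregnancy test is at Baseline, so up to three further doses could be given to a woman of childbearing potential without a new test

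*Protocol*

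**What the plan says.** **The test.** Protocol Section 6.7 states: "Urine pregnancy tests will be performed on all women at Baseline prior to the dose of study drug". A positive urine result is confirmed with a blood test. Inclusion criterion 7 asks for a negative test at Baseline. In Appendix 1 the pregnancy-test row has one mark, under Baseline (Day -7). The dosing column (Day 1, or Day 8 after a failed tracer synthesis) has none, although physical examination, vital signs, safety bloods and urinalysis are all marked there at time 0.

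**The doses.** Sections 3.1, 3.4 and 5.2 allow up to four doses per participant. Section 3.1 sets a washout of at least 14 days between doses. If the tracer cannot be made on the day, "participants will wait at least 1 week before another dose of PLN-74809 is administered". Post-dose PET scans are capped at two.

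**The waiver.** For later doses, if the Investigator sees no clinical decline, the synopsis says "only hematology and clinical chemistry assessments should be completed; other Screening and Baseline procedures are not required" and mentions 60 days. Section 3.1 and Appendix 1 footnote m say "the other Screening and Baseline procedures do not have to be repeated" and give no time limit. Footnote m is written for participants testing two dose levels.

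**Who is concerned.** Inclusion criterion 8 admits women of childbearing potential who use contraception. Pregnancy is exclusion criterion 18. Under Section 6.10.6, a pregnancy after dosing must be notified to the Sponsor within 24 hours.

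**The concern.** Section 6.7 reads as though there were a single dose, while the current design allows four. The pregnancy test is a Baseline procedure, and Baseline procedures as a class need not be repeated. The condition for the waiver, no clinical decline, concerns the course of the lung disease and cannot detect a pregnancy. The only work that the synopsis keeps is hematology and clinical chemistry, and the chemistry panel in Appendix 2 contains no pregnancy marker.

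A site could therefore follow the readable text exactly and give a second, third or fourth dose of an investigational drug on a test that is several weeks old. The protocol treats pregnancy as a bar to entry and as a reportable event after dosing, so a stale test before later doses falls short of its own standard. What is at stake is the safety of a participant and a possible pregnancy. No estimate or analysis population depends on it.

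**Working it through.** The documents give no age for the test, so there is no stated figure to reproduce. What follows is calendar arithmetic on minimum intervals.

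**Inputs**
- Baseline test on Day -7 (Protocol Section 3.4, Appendix 1).
- First dose on Day 1. SAP Section 6.2.9 has no Day 0, so Day -7 is 7 days before Day 1.
- Minimum gap between doses: 14 days for a washout, 7 days after a failed synthesis (Protocol Section 3.1).
- At most four doses and at most two post-dose scans (Protocol Section 3.1).

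**Formula.** Minimum age of the test at dose *k* = 7 + the sum of the *k* − 1 minimum gaps before it.

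| Dose | Every gap 7 days | Every gap 14 days |
|---|---|---|
| 1 | 7 | 7 |
| 2 | 7 + 7 = 14 | 7 + 14 = 21 |
| 3 | 7 + 2 × 7 = 21 | 7 + 2 × 14 = 35 |
| 4 | 7 + 3 × 7 = 28 | 7 + 3 × 14 = 49 |

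**Which figures apply at dose 4.** The summary of Amendment 5 says that the allowance of four doses was brought in to cover failed tracer synthesis. With at most two post-dose scans, at least one of the first three doses must have had no scan. If the 1-week rule applies after each failed synthesis, and the 14-day washout after each scanned dose, then:
- no earlier dose scanned: 7 + 7 + 7 + 7 = 28 days;
- one earlier dose scanned: 7 + 14 + 7 + 7 = 35 days;
- two earlier doses scanned: 7 + 14 + 14 + 7 = 42 days.

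The dose 4 minimum is therefore 28 to 42 days. If dose 4 is given to obtain a scan that is still allowed, at most one earlier dose was scanned, and the range is 28 to 35 days. The figure of 49 days needs a 14-day washout at every gap, including after a failed synthesis.

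**Sensitivity.** All of these are minimums. Screening and Baseline may fall on the same day. If one assumes that this could be as early as Day -35, the test is 35 days old at dose 1. It is then at least 35 + 7 = 42 days old at dose 2 after a 1-week wait, and 35 + 3 × 14 = 77 days old at dose 4 with a washout at every gap. The documents do not say whether Baseline may move that early.

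**Number of doses and tests.** Doses after the first: 4 − 1 = 3. Upper bound on added tests if only those doses are covered: 12 participants × 3 = 36.

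**The case against.** The strongest objection is that the governing section cannot be read. Section 3.4 sends the reader to Section 5.5 for additional doses. The contents list shows that section, but its text is not in the public copy. It may require a repeat test, and a specific body section could properly qualify a synopsis sentence. This stands. The conclusion has to be limited to what a site could do on the readable text, and a reader should not infer that the full protocol lacks a repeat test.

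A reader might also infer that the plan expressly waives the pregnancy test. It does not. No waiver sentence names the test, and the wording in Section 3.1 and footnote m permits omission without requiring it. The test is caught only because it belongs to the class of Baseline procedures.

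It is tempting to add that eligibility is not checked again before later doses. The "Check inclusion exclusion criteria" row supports this only weakly. The columns of the SAP copy do not line up in the public text, and the Protocol copy has a stray character at time 0. The point does not need this row.

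A further objection is that a check before each tracer injection may sit in the Radiology Manual, which is not available here. It may, but it would not close the gap. Section 6.9.1 puts the scan at least 4 hours after study drug, and a dose followed by failed synthesis has no scan. A participant given four doses has at least 4 − 2 = 2 doses without one.

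Finally, the risk is small: entry at age 40 or older, no more than 12 participants, and contraception required. This stands and sets the weight of the point.

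**Conclusion.** The concern holds in a limited form. On the readable text, the pregnancy test is scheduled once, and the general waiver lets it go unrepeated before up to three further doses. The minimum age of the test is 14 or 21 days at dose 2, depending on whether a failed synthesis or a washout came before. At dose 4 it is 28 to 42 days if the 1-week rule applies after failed syntheses. A reader might take 49 days as the usual figure. The documents do not support that, because doses 3 and 4 exist mainly for failed syntheses, which carry the shorter wait.

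The conclusion assumes that Section 5.5 adds no test and that Baseline is on Day -7. If Section 5.5 does require a repeat test, what remains is an inconsistency between it and the synopsis, Section 3.1, footnote m and Appendix 1, which a site could resolve the wrong way.

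The number of women of childbearing potential is not given and may be zero, so the number affected cannot be estimated. The documents do not support an inference that any participant would be harmed or that the results would be biased. The weight is low: a safeguard worth considering, with no effect on the analysis.

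**What to change.** - In Section 6.7 and Appendix 1, require a negative urine pregnancy test in women of childbearing potential before study drug on each additional dosing day. Testing again before dose 1 is optional.
- In the synopsis, Section 3.1 and footnote m, exempt this test from the waiver of repeat procedures.
- If Section 5.5 already requires the test, align these places with it.

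No new visit or sample is needed. Appendix 1 already marks urinalysis at time 0 of the dosing day, described as "Urinalysis: dipstick followed up by microscopic examination if needed", and the pregnancy test can use the same urine. The added load is at most 12 × 3 = 36 tests, or 12 × 4 = 48 if dose 1 is included. Both bounds assume that every participant is a woman of childbearing potential who receives four doses, so the real number would be far lower. The downside is that a positive result delays the dose until the blood test is back and may waste the tracer batch made for that day.
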